4.3. Viral Challenge Exclusion Criteria

Any potential subject who meets any of the following criteria on entry to the quarantine Unit on Day -2 or -1 will be excluded from participating in the viral challenge.

1. Subject has acute illness within 7 days of admission (this does not include minor illnesses such as diarrhea). Subjects can be rescheduled for another viral challenge admission day if possible and the protocol window permitting.
2. Subject has a temperature ≥ 37.8 °C on Day 0, the day of viral challenge. Subjects can be rescheduled for another viral challenge admission day if possible and the protocol window permitting.
3. Subjects having donated or lost more than 1 unit of blood (470 mL) within 60 days or more than one unit of plasma within 7 days.
4. Subjects with active acute respiratory infection.
5. Subject has any clinically significant abnormalities (ECG, vital signs).
6. Subjects having received an investigational agent (small molecule) or vaccine (other than study vaccine) within 30 days, or having received a biological product other than a vaccine within 3 months or 5 half-lives (whichever is longer) prior to entry to the quarantine Unit.
7. All female subjects must have a negative highly sensitive serum β -hCG pregnancy test on admission.
8. Subjects with a positive urine drug test. On admission, urine will be tested for the presence of amphetamines, benzodiazepines, cocaine, cannabinoids, opioids, methadone, and barbiturates. *Note:* A positive urine drug test may be repeated once in the same sample, as soon as possible, to exclude a technical error. Subjects with a negative urine drug test at retest may be included.

9. Male subjects must agree to the contraceptive requirements below at entry to the quarantine Unit, and continuing until 3 months after the date of viral challenge:
- Use a condom and spermicide (for all partners)
 - Male sterilization with the appropriate post-vasectomy documentation of the absence of sperm in the ejaculate (note that the use of condom with spermicide will still be required to prevent partner exposure)
 - In addition, for female partners of childbearing potential, that partner must use another form of contraception such as:
 - Established (a minimum of 2 weeks prior to admission) use of oral, injected or implanted hormonal methods of contraception
 - Placement of an intrauterine device (IUD) or intrauterine system (IUS)
 - Barrier methods of contraception or occlusive cap (diaphragm or cervical/vault caps), both with one of the following: spermicidal foam/gel/film/cream/suppository
 - Bilateral tubal ligation
 - True abstinence – when this is in line with the preferred and usual lifestyle of the subject

In addition to the contraceptive requirements above, male subjects must agree not to donate sperm following discharge from quarantine until 90 days after the date of viral challenge.

4.4. Prohibitions and Restrictions

Potential subjects must be willing and able to adhere to the following prohibitions and restrictions during the course of the study to be eligible for participation:

- 1 Agree to follow all requirements that must be met during the study as noted in the inclusion and exclusion criteria (Section 4.1 and Section 4.2, respectively).
- 2 Vaccination with live attenuated vaccines within 28 days of a study vaccination and the viral challenge (ie, before and after) is prohibited. Other vaccines (eg, influenza, tetanus, hepatitis A, hepatitis B, rabies) should be given at least 14 days before (or at least 14 days after) administration of study vaccine and the viral challenge in order to avoid potential confusion of adverse reactions and potential immune interference. If a vaccine is indicated in a post-exposure setting (eg, rabies or tetanus), it must take priority over the study vaccine.
- 3 Subjects may not use drugs such as amphetamines, benzodiazepines, cocaine, cannabinoids, barbiturates, opiates, and methadone from 3 months prior to ICF signature until completion of the last study-related activity. Refer to Section 8, for details regarding prohibited and restricted therapy during the study.
- 4 Subjects must not donate blood for 3 months after completion of the study.

- 5 Subjects must not consume any food containing poppy seeds or any codeine containing formulation starting 72 hours before screening and before admission to the quarantine Unit (in order to avoid false-positive urine drug screen).
- 6 Subjects must not smoke or otherwise use tobacco products from 30 days prior to entry to the quarantine Unit and must continue to abstain from smoking until the completion of the last study-related activity.
- 7 To reduce the risk of passing RSV on to others, subjects will be advised to avoid contact with the following vulnerable groups of people for two weeks after leaving the quarantine Unit:
 - any person with any known immunodeficiency
 - any person receiving immunosuppressant medications
 - any person undergoing or soon to undergo cancer chemotherapy
 - any person who has congestive heart failure or is in frail health
 - any person who has a diagnosis of emphysema or COPD, is elderly residing in a nursing home, or has severe lung disease
 - any person who has received a transplant (bone marrow or solid organ)
 - children below the age of 1 year
 - elderly persons (aged 75 years or older).

5. STUDY VACCINE ALLOCATION AND BLINDING

Study Vaccine Allocation

Within each cohort, subjects will be randomized 1:1 to one of the two groups (Ad26.RSV.preF or placebo). Randomizations will be based on computer-generated schedules prepared before the study by or under the supervision of the sponsor. The randomizations will be balanced by using randomly permuted blocks.

A unique code will dictate the study vaccine assignment for the subject.

Withdrawal of randomized subjects from vaccination before vaccination: Additional subjects will be recruited and immunized to replace these withdrawn subjects at the discretion of the sponsor. The replacement subject will be assigned to the same group as the original (discontinued) subject. The replacement subject's randomization number will equal the randomization number of the discontinued subject +100 (for example subject 0001 would be replaced by subject 0101).

As approximately 44 subjects need to be challenged, initially 4 more subjects in the first cohort will be randomized (overflow subjects). If subjects withdraw between vaccination and challenge, the unblinded pharmacist will make every effort to replace this subject with an overflow subject

of the same group as the withdrawn subject if possible. The withdrawal rate between vaccination and challenge for the first cohort will be used to assess how many extra subjects will need to be vaccinated for subsequent cohorts. Any subject who experiences an SAE before admission to the Unit will not be challenged and will be replaced.

Blinding

The investigator will be provided with a sealed randomization code for each subject, containing coded details of study vaccine allocation. All randomization codes, whether opened or sealed, will be collected after the end of the subject's participation in the study.

Under normal circumstances, the blind should not be broken until all subjects have completed the study and the database is finalized. While the responsibility to break the study vaccine allocation code in emergency situations resides solely with the investigator, it is recommended that the investigator contacts the sponsor or its designee if possible to discuss the particular situation, before breaking the blind. Telephone contact with the sponsor or its designee will be available 24 hours per day, 7 days per week. In an emergency situation, the investigator may determine the identity of the study vaccine by opening the sealed code. In the event the blind is broken, the sponsor must be informed as soon as possible. The date, time and reason for the unblinding must be documented in the appropriate section of the electronic case report form (eCRF). The investigator is advised not to reveal the study vaccine assignment to the study-site personnel or sponsor personnel. If the code is broken by the investigator or the study-site personnel, the subject must be withdrawn from the study and must be followed as appropriate. If the code is broken by the sponsor for safety reporting purposes, the subject may remain in the study.

The subjects, study-site personnel (including the vaccine administrator), and investigator will be blinded to study vaccine allocation throughout the study, except for the unblinded pharmacist or qualified staff member with primary responsibility for study vaccine preparation and dispensing.

At the end of the quarantine phase for the final cohort, the sponsor will request the treatment codes for the primary analysis. However, treatment codes will not be disclosed to the investigator and subject(s).

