10.2. Discontinuation from Challenge Phase/Withdrawal from the Study

Discontinuation from Challenge Phase

Subjects will be discontinued prior to the viral challenge phase (ie, pre-inoculation) for the reasons listed below. These subjects must not receive the viral challenge but should continue other study procedures, eg, safety follow-up:

- Pregnancy
- Any SAE
- Any related AE, worsening of health status or intercurrent illness that, in the opinion of the investigator, precludes the subject from viral challenge
- The randomization code is broken by the investigator or the study-site personnel

Overflow subjects from the first cohort will be challenged in subsequent cohorts. Any subject who is vaccinated in subsequent cohorts but not challenged will be followed to the end of the study.

Withdrawal from the Study

Each subject has the right to withdraw from the study at any time for any reason without affecting the right to treatment by the investigator. Although the subject is not obliged to give a reason for withdrawing prematurely, the investigator should make a reasonable effort to ascertain the reason(s) while fully respecting the subject's rights.

A subject will be withdrawn from the study for any of the following reasons:

- Repeated failure to comply with protocol requirements
- Decision by the sponsor or the investigator to stop or cancel the study
- Decision by local regulatory authorities and Institutional Review Board/Independent Ethics Committee (IRB/IEC) to stop or cancel the study
- Lost to follow-up
- Withdrawal of consent

- Death

Any unnecessary study discontinuation should be avoided. Should a subject be withdrawn, all efforts should be made to complete and report the observations as thoroughly as possible. Whenever a subject is withdrawn from the study, independent of the reason, a final evaluation should be completed for that subject and the major reason for which the subject was withdrawn must be stated. If a subject is lost to follow-up, every reasonable effort must be made by the study-site personnel to contact the subject and determine the reason for withdrawal. The measures taken to follow-up must be documented.

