11.1. Analysis Sets

The **Full Analysis (FA) Set** includes all subjects who were randomized and received study vaccine, regardless of the occurrence of protocol deviations. Vaccination assignment will follow the as-treated principle. All safety and subject information analyses will be based on the FA set. As a sensitivity analysis, key immunogenicity tables will also be based on the FA set.

The **Intent-to-Treat-Challenge (ITTc)** population is a subset of the FA set that includes all randomized, vaccinated and challenged subjects. All efficacy analyses will be performed on the ITTc population. Important subject information tables might be repeated based on the ITTc population as well.

The **Per-protocol Immunogenicity (PPI) Set** will include all randomized and vaccinated subjects for whom immunogenicity data are available, excluding subjects with major protocol deviations expecting to impact the immunogenicity outcomes.

In addition, for subjects who experience a natural RSV infection (based on RT-PCR, or other sources), samples taken after the natural infection will not be included in the PPI set.

The analysis of immunogenicity will be based on the PPI set.

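### A code break at the site means study withdrawal in Protocol Section 5 but continued follow-up in Section 10.2; after inoculation only the withdrawal rule exists, and the SAP does not say how that subject's VL-AUC is derived

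*Protocol*

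**What the plan says.** Protocol Section 5 (Blinding) leaves emergency unblinding to the investigator and then states: "If the code is broken by the investigator or the study-site personnel, the subject must be withdrawn from the study". The sentence goes on to require follow-up as appropriate. If the sponsor breaks the code for safety reporting, the subject may stay in.

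Protocol Section 10.2 has two lists. The first concerns discontinuation from challenge: "Subjects will be discontinued prior to the viral challenge phase (ie, pre-inoculation) for the reasons listed below". One of its reasons is "The randomization code is broken by the investigator or the study-site personnel", and its consequence is "These subjects must not receive the viral challenge but should continue other study procedures, eg, safety follow-up". The second list opens "A subject will be withdrawn from the study for any of the following reasons" and gives six reasons; a code break is not one of them.

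For anyone who is withdrawn, Section 10.2 adds: "Whenever a subject is withdrawn from the study, independent of the reason, a final evaluation should be completed". Section 9.1.8 provides an early exit visit with the Day 28 procedures, but takes safety laboratory samples there only within 7 days of vaccination. Section 12.3.2 keeps unresolved SAEs under follow-up after participation ends.

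The efficacy set, ITTc, "is a subset of the FA set that includes all randomized, vaccinated and challenged subjects" (Protocol Section 11.1; SAP Section 3.3.2 agrees). SAP Section 6.1 sums trapezoids of log10 viral load up to the last available value before discharge and does not divide by duration. SAP Section 6.1.1 sets a missing first or last timepoint to 0 and imputes nothing else.

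**The concern.** There are two separate problems.

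Before inoculation, the same trigger has opposite consequences. Under Section 10.2 the subject stays in follow-up, so the remaining 28-day adverse-event data, the immunogenicity samples and the 6-month SAE contact are kept. Under Section 5 the subject leaves the study. Which data exist for that subject would depend on which page the site read.

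After inoculation there is no contradiction, because only Section 5 speaks. Read literally, withdrawal ends the remaining 12-hourly nasal washes, symptom cards, mucus collection, spirometry, the ECGs and cardiac enzymes still due on Days 3, 7 and 11, the discharge laboratory tests, the Day 28 visit as scheduled and the 6-month call. The subject nevertheless stays in ITTc, so the primary endpoint is incomplete because of a rule. Section 5 links site code breaks to emergencies, so the loss could be related to outcome. RT-PCR viral load is a laboratory measurement, and knowledge of the arm is not in itself a reason to stop collecting it.

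**Working it through.** **1. The two rules side by side**

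| Time of site code break | Section 5 | Section 10.2 | In ITTc? |
|---|---|---|---|
| After vaccination, before inoculation | Withdrawn from study | Not challenged; other procedures continue; not a withdrawal reason | No (never challenged) |
| After inoculation | Withdrawn from study | Silent | Yes |

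Row 1 is a contradiction, but it cannot affect VL-AUC, because the subject is never challenged. Row 2 affects VL-AUC, but rests on Section 5 alone.

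**2. Safety data after a post-inoculation withdrawal**

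Challenge is at least 24 days after vaccination, and exit laboratory samples are limited to 7 days after vaccination. Since 24 > 7, an exit after challenge includes no safety laboratory tests. The exit visit itself, the final evaluation and follow-up of unresolved SAEs remain.

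**3. What happens to one subject's AUC**

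The documents give no curve, so two triangular log10 curves are assumed, each lasting 8 days: peak Day 6 (Day 2.5 to 10.5) and peak Day 7 (Day 3 to 11). With the peak set to 1, the full area is 0.5 × 8 = 4, and the percentages do not depend on the height.

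The SAP rule can be read in two ways:
- Reading A: the last timepoint is the subject's own last sample, so the sum stops there.
- Reading B: the last timepoint is the last planned sample (taken as Day 11.5). It is set to 0, and the formula joins the last observed value to it by a straight line.

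Example, peak Day 6, last sample Day 4:
- Height at Day 4 is 1.5/3.5 = 0.429.
- Reading A: 0.5 × 1.5 × 0.429 = 0.321; 0.321/4 = 8%.
- Reading B adds 0.5 × (11.5 − 4) × 0.429 = 1.607; (0.321 + 1.607)/4 = 48%.

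Example, peak Day 6, last sample Day 6:
- Reading A: 0.5 × 3.5 × 1 = 1.75; 1.75/4 = 44%.
- Reading B adds 0.5 × 5.5 × 1 = 2.75; 4.50/4 = 112.5%.

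| Last sample | Reading A (peak Day 7, peak Day 6) | Reading B (peak Day 7, peak Day 6) |
|---|---|---|
| Day 4 | 3%, 8% | 27%, 48% |
| Day 6 | 28%, 44% | 80%, 112.5% |
| Day 8 | 72%, 83% | 105%, 107% |

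The AUC may be far too low or somewhat too high.

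**4. What one subject can do to the test**

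The plan's own figures come first (Protocol Section 11.2: 22 per arm, mean 320, SD 275). The normal approximation is power = Φ(δ/(SD√(2/n)) − z), with 275 × √(2/22) = 82.9:
- 50% reduction, one-sided 20%: 160/82.9 − 0.842 = 1.088, power 86.2%.
- 75% reduction, one-sided 5%: 240/82.9 − 1.645 = 1.250, power 89.4%.

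Both agree with the stated 80% or more, which is not disputed here.

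As an outer limit on the low side, one subject's AUC was set to 0, which is harsher than either reading in the table. Inputs to the simulated rank-sum test (40,000 trials, tie-corrected normal approximation): 35% zeros in placebo and 320/275 taken as the overall mean and SD, so the infected mean is 320/0.65 = 492 and SD about 178.

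| Scenario under no vaccine effect | Nominal 20% | Nominal 5% |
|---|---|---|
| One random vaccine subject set to 0 | about 25% | about 6.9% |
| One random placebo subject set to 0 | about 15% | about 3.3% |
| Vaccine subject with the highest AUC set to 0 | about 34% | about 11% |

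At a 50% reduction and the 20% level, power moves from 86–88% to 80–85% (random placebo subject) or 88–90% (random vaccine subject).

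**The case against.** The strongest reply is that this is a minor wording conflict plus a design choice. Four stronger readings are tempting, and the documents do not support them.

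- **The contradiction truncates the primary endpoint.** It does not. Section 10.2 is expressly limited to the period before inoculation, and those subjects have no VL-AUC.
- **Withdrawal ends safety follow-up.** It ends scheduled visits. Section 5 still requires follow-up as appropriate, Section 10.2 a final evaluation and every effort to complete observations, Section 9.1.8 an exit visit, Section 9.2.6 follow-up of clinically significant abnormalities, and Section 12.3.2 follow-up of unresolved SAEs. Nor does any sentence say that nasal washes stop; that is the ordinary meaning of withdrawal.
- **The AUC is always biased towards the uninfected.** The zero rule can raise it, as the working shows.
- **The unblinded subject will be the sickest.** The documents do not say so and give no code-break frequency. Section 1.2 describes symptoms in this model as mild. Section 17.9.2 provides for ending the whole study, after discussion, for severe or clinically significant illness from challenge; one incomplete curve would then be secondary.

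The different treatment of site and sponsor code breaks also has a rationale. A site break unblinds the people who review symptom cards and judge causality; a sponsor break for safety reporting need not.

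What stands is the conflict before inoculation, the silence of Section 10.2 after it, and the lack of a clear VL-AUC rule for a subject who leaves early.

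**Conclusion.** The point holds in two separate parts. Sections 5 and 10.2 contradict each other for a site code break before inoculation and must be reconciled; what is at stake there is safety and immunogenicity follow-up, not the primary endpoint. After inoculation, Section 5 alone, read literally, stops scheduled data collection in a subject who remains in ITTc. That subject's VL-AUC can be wrong in either direction: 3% to about 112% of its complete value across the days, curves and readings tried.

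One random subject at the extreme low end would move the nominal 20% and 5% error rates to about 25% and 6.9%, or to 15% and 3.3%, depending on the arm. These figures rest on assumed curves, on 320/275 describing all placebo subjects, and on exactly one affected subject. They show sensitivity and do not forecast an effect. Because the event is probably rare, this is a change that should be made rather than a defect that undermines the design.

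**What to change.** Reconcile Section 5 with Section 10.2 so that a code break is not in itself a reason to end data collection. Before inoculation, let Section 10.2 govern. After inoculation, continue the scheduled assessments as far as clinically feasible in the investigator's judgement, unless consent is withdrawn or another Section 10.2 withdrawal reason applies. This concerns data collection only; it takes no position on clinical care after an emergency and leaves the rule on challenge untouched.

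In the SAP:
- keep the subject in ITTc and carry the unblinding date, already recorded in the eCRF, as a flag in the analysis data;
- repeat the symptom summaries without symptom-card entries made after unblinding;
- state how VL-AUC is derived for a subject who leaves early, including whether the last timepoint in the zero rule means the last planned or the last observed sample.

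The cost is a short change to Section 5 and a few lines in the SAP, with no new procedures. The small downside is that symptom reports and causality judgements after unblinding are open-label. The flag identifies the affected symptom entries but does not remove the effect on causality judgements.

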6. DOSAGE AND ADMINISTRATION

Ad26.RSV.preF will be supplied at a concentration of 1×10^{11} vp/0.5 mL in single-use vials, with an extractable volume of 0.5 mL, for intramuscular injection into the deltoid of the non-dominant arm. A dose level of 1×10^{11} vp will be used.

Placebo will be supplied as sterile 0.9% saline for injection.

For each subject, every vaccination will be 0.5 mL in volume.

An unblinded pharmacist, or other qualified individual will prepare the appropriate vial and syringe and provide the syringe in a blinded manner to the study vaccine administrator who will perform the injection.

Note: the unblinded pharmacist, or other qualified individual, may also perform the administration, but will have no other study function.

Further details on study vaccine preparation will be provided in the Investigational Product Preparation Instructions.

7. STUDY VACCINE COMPLIANCE

Study vaccine will be administered intramuscularly by a study vaccine administrator – a trained and qualified study nurse, medical doctor, or otherwise qualified health care professional. The date and time of study vaccine administration will be recorded in the eCRF.

8. PRE-STUDY AND CONCOMITANT THERAPY

Pre-study therapies administered up to 90 days before vaccination must be recorded in the eCRF at vaccination.

Concomitant therapies will be collected and recorded in the eCRF from time of study vaccine administration until 28 days after vaccination, and from the entry into the Unit until 28 days after challenge, and additionally outside of these periods when associated with an SAE meeting the criteria outlined in Section 12.3.2. Information on concomitant use of herbal supplements or vitamins will not be collected.

Use of any experimental medication (including experimental vaccines other than the study vaccine) during the study is not allowed.

Subjects can receive medications such as acetaminophen, non-steroidal anti-inflammatory drugs (NSAIDs), or antihistamines as needed, although their use must be documented and use of these medications as routine prophylaxis prior to study vaccination is discouraged, unless if specified by the sponsor. All other concomitant therapies should also be recorded if administered in conjunction with new or worsening AEs reported per protocol requirements outlined in Section 12.3.1).

Chronic (longer than 10 days) or recurrent use of systemic corticosteroids is prohibited during the study and within 6 months before administration of study vaccine (*Note:* ocular, topical or inhaled steroids are allowed). Antineoplastic and immunomodulating agents or radiotherapy are prohibited in the 9 months prior to vaccination and during the study.

After the viral challenge, paracetamol, oral contraception and thyroxin, if already prescribed before entry to the Unit, are allowed concomitant medications.

If chronic use of prohibited therapies becomes medically indicated during the course of the study for any subject, the sponsor should be contacted.

Vaccination with live attenuated vaccines within 28 days of a study vaccination and the viral challenge (ie, before and after) is prohibited. Other licensed vaccines (ie, not live) should be given at least 14 days before or at least 14 days after administration of study vaccine and the viral challenge in order to avoid potential confusion of adverse reactions and potential immune interference. If a vaccine is indicated in a post-exposure setting (eg, rabies or tetanus), it must take priority over the study vaccine.

The sponsor must be notified in advance (or as soon as possible thereafter) of any instances in which prohibited therapies are administered.

